6.4 Study Procedure Risks

6.4.1 Endoscopy and pharyngeal distensibility measurement

Will be performed under sedation at Day Surgery Unit, St George Hospital. A combination of sedative drugs (fentanyl, midazolam, and propofol) will be administered by an anaesthetic team led by an experienced anaesthetic consultant. Such sedation has small potential risk relating cardiac/respiratory function and drug allergic reactions. These risks are managed and minimised by a pre-anaesthetic consultation with anaesthetic consultants, during which any potential issue will be identified and addressed. Participants will only proceed with this procedure if it is deemed safe. During the procedure, participants will be monitored constantly to ensure safety.

Endoscopy involved in this procedure is a diagnostic (non-interventional) procedure utilising standard endoscope (Olympus H190 gastroscope). Thus, no significant risk is anticipated. Pharyngeal distensibility is performed following the endoscopy using a flexible catheter (EndoFLIP) approved for clinical use. Pharyngo-oesophageal distensibility measurement using this technique have been shown to be safe with no known risk to participants [21, 22]. Our laboratory has extensive experience with this technique in over 200 cases confirming its safety [8].

6.4.2 Pentoxifylline (TRENTAL 400) - adverse events

Source TGA Product Information (last amended 25 September 2015)

The following adverse effects have been reported in clinical trials or post-marketing with Trental 400 with dosages of 400 mg two to three times daily, with treatment periods up to 60 weeks

Gastrointestinal

The most frequent (greater than 1% incidence) types of side effects seen with Trental (all formulations) were gastrointestinal upsets, including nausea, dyspepsia, vomiting, belching/flatus/bloating, abdominal pain, epigastric discomfort and diarrhoea. However, the controlled release preparation of Trental 400 resulted in much fewer gastrointestinal side effects, the most common being dyspepsia 2.8% (placebo 4.7%), nausea 2.2% (placebo 0.8%), vomiting 1.2% and belching/flatus/bloating (0.6%). Anorexia, cholecystitis, constipation and a dry mouth/thirst have been reported with a frequency of less than 1%.

Central Nervous System

Side effects related to C.N.S. disturbances with an incidence of greater than 1% included dizziness, headache, insomnia and sleep disturbances and disorders, blurred vision, agitation/nervousness, drowsiness and tremor. Of these, the following were reported for the controlled release preparation Trental 400: dizziness 1.9% (placebo 3.1%), headache 1.2% (placebo 1.6%) and tremor 0.3% (placebo 0.8%). Anxiety and confusion have been reported with a frequency of less than 1%. Isolated cases of aseptic meningitis have been reported.

Cardiovascular

Only angina/chest pain was reported for Trental 400 tablets, with an incidence of 0.3%, while for the capsule formulation flushing and arrhythmia/palpitation/tachycardia were also reported, with an incidence of greater than 1%. Reports of hypotension were rare (<0.1%). Dyspnea and oedema have been reported with a frequency of less than 1%. Haemorrhage has also been reported (frequency unknown).

Hepatic

Isolated cases of intrahepatic cholestasis and jaundice as well as hepatitis and transaminase elevation have been reported.

Haemic and Lymphatic

Decreased fibrinogen, pancytopenia, purpura, aplastic anaemia, neutropenia and leukopenia. Isolated cases of thrombocytopenia have been noted

Respiratory

Epistaxis, flu-like symptoms, laryngitis and nasal congestion have been reported rarely.

Hypersensitivity

Anaphylactic and anaphylactoid reactions have been reported. Pruritus, rashes and urticaria may occur with a frequency of 0.1% to 1% but progression to anaphylactoid shock (angioedema, bronchospasm) occurs only in isolated cases. Erythema (reddening of the skin) has been reported at an unknown frequency.

Miscellaneous

Rarely, the following were reported: brittle fingernails, blurred vision, conjunctivitis, earache, scotoma, bad taste in the mouth, excessive salivation, malaise, sore throat, swollen neck glands, weight change.

6.4.3 Vitamin E (TOCOPHEROL) - Adverse events

Vitamin E is generally considered safe and is available without prescription. The recommended upper limit of Vitamin Supplementation is based on haemorrhagic effects observed in animals given very high doses. Human trials fail to demonstrate consistently an association between excess α -tocopherol intake and haemorrhagic stroke or breathing. However, since both substances exhibit haemorrhological effects patients with history of GI bleeding, impaired clotting and previous haemorrhagic stroke will be excluded from the study.

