4.4 Treatment

- 1) Compounded tablets of Pentoxifylline and Vitamin E, three times a day for 12 weeks, combined daily dose of 1,200mg of Pentoxifylline and 1,000IU Vitamin E Succinate

Or

- 2) Identical placebo tablets

Active and placebo drugs will be supplied by STENLAKE compounding chemist.

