5.2 Exclusion criteria

- Individuals who cannot provide informed consent due to any reason (language barrier, impaired cognitive function)
- Recurrence or persistent disease following head and neck cancer treatment.
- Pre-existing disorder known to cause pharyngeal dysphagia such as: MVA, MND, Parkinson's, inflammatory myopathy.
- Pre-existing oesophageal disease known to cause dysphagia such as eosinophilic oesophagitis, achalasia, oesophageal cancer.
- Either current pregnancy, intended pregnancy or breastfeeding during the study
- History of severe haemorrhage, e.g. massive retinal haemorrhage, cerebral haemorrhage, acute myocardial infarction or recent history of peptic ulcer.
- Concomitant or recent use of Warfarin or impaired blood clotting.
- Previous intolerance to Pentoxifylline or other methylxanthines such as caffeine, theophylline, and theobromine.
- Significant impairment of renal or hepatic function or other co-morbid conditions which in the opinion of the investigators preclude inclusion in the study

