5.3 Clinician screening guideline

Refer to Screening Guideline v1.0 document to flag participants with increased risk of adverse events and drug interaction for close monitoring.

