6.5 Recruitment and Screenings

Potential participants with suspected pharyngeal stricture where endoscopic dilatation is indicated will be identified and screened for eligibility at Swallow Clinic (A/[name], [name], [name]) or during post-cancer-treatment visits at Cancer Care Centre (A/[name], A/[name]).

SSQ will be used as a clinical assessment to quantify swallow impairment in post-laryngectomy patients. Score >234 will indicate pharyngeal dysphagia and suitability for this study. Potential participants will then be screened for exclusion criteria (see 5.2).

Screening will be completed after consent as presence of a stricture can only be truly identified during endoscopy while patient is sedated. If participant is eligible they will be enrolled into the study.

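### Section 6.4.3 promises to exclude anyone with past gastrointestinal bleeding, but the exclusion list in 5.2 lets a non-severe past bleed through

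*Protocol*

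**What the plan says.** Section 6.4.3, in the account of vitamin E risks, makes a commitment about who will be kept out: "since both substances exhibit haemorrhological effects patients with history of GI bleeding, impaired clotting and previous haemorrhagic stroke will be excluded from the study". It sets no limit on how severe or how recent a GI bleed must be.

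The formal list is in section 5.2. Its two bleeding-related entries are "History of severe haemorrhage, e.g. massive retinal haemorrhage, cerebral haemorrhage, acute myocardial infarction or recent history of peptic ulcer" and "Concomitant or recent use of Warfarin or impaired blood clotting". A later entry allows exclusion for "other co-morbid conditions which in the opinion of the investigators preclude inclusion in the study".

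Section 6.5 names the list that screeners use: "Potential participants will then be screened for exclusion criteria (see 5.2"). It does not mention 6.4.3. Section 5.3 adds a separate screening guideline, whose stated purpose is "to flag participants with increased risk of adverse events and drug interaction for close monitoring".

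**The concern.** The two sections set different entry rules for the same safety risk, and the narrower rule is the one used at screening. If 6.4.3 states the intended safeguard, screening does not deliver it.

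Dilatation is routine care for these patients, so the risk that the trial adds is the study drug. Section 4.4 gives 12 weeks of treatment at a "combined daily dose of 1,200mg of Pentoxifylline and 1,000IU Vitamin E Succinate". For pentoxifylline, section 6.4.2 records: "Haemorrhage has also been reported (frequency unknown"). Section 6.4.3 itself gives the drugs' effects on blood as the reason for the exclusion. Treatment starts after dilatation (6.2), and dilators are passed until a mucosal tear is seen or resistance is met (6.3.3), so some participants may start the drug soon after an upper-tract tear.

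There is also a consequence for the pilot's own outputs. Section 8.2 lists protocol violations among the feasibility measures. Enrolling a patient with a minor past GI bleed complies with 5.2 and contradicts 6.4.3, so it is unclear whether to count it as a violation.

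**Working it through.** No arithmetic applies beyond a count, and the plan has no figure to reproduce. The check sets 6.4.3 against 5.2 item by item and then traces the group on which they differ.

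**Step 1: the three conditions in 6.4.3 against the mandatory entries in 5.2**

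| Condition in 6.4.3 | Counterpart in 5.2 | Coverage |
|---|---|---|
| Impaired clotting | Named in the warfarin and clotting entry | Full |
| Previous haemorrhagic stroke | Cerebral haemorrhage, in the haemorrhage entry | Full |
| History of GI bleeding | Not named; caught only as severe haemorrhage or through a recent peptic ulcer | Partial |

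Two of three conditions are fully carried over and one only in part.

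**Step 2: patients with a past GI bleed, by type**

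| Past GI bleed | Excluded by 6.4.3? | Mandatory exclusion in 5.2? |
|---|---|---|
| Severe | Yes | Yes |
| Not severe, with a recent peptic ulcer | Yes | Yes |
| Not severe, no recent ulcer, but warfarin or impaired clotting | Yes | Yes |
| Not severe, no recent ulcer, no warfarin, normal clotting | Yes | **No** |

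The last row is the gap. The haemorrhage entry in 5.2 introduces its list as examples, which leaves the site of bleeding open, but the requirement that the bleed be severe remains.

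**Step 3: whether another provision closes the gap**

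- The co-morbidity clause in 5.2 depends on investigator opinion. It permits exclusion but does not require it, whereas 6.4.3 is unconditional.
- The guideline in 5.3 is described as a means of identifying patients for closer monitoring. On that description it does not exclude anyone.
- Section 6.5 points to 5.2 alone.

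**Step 4: size**

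The trial plans 40 participants, 20 per group (4.5), allocated 1:1 (section 7). The protocol gives no frequency of past GI bleeding in this population, and none is assumed here. If k such patients enrol, about k/2 would be expected on active drug.

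**The case against.** The strongest reply is that the protocol should be read as a whole. Section 6.4.3 binds the same investigators as 5.2, and it can inform their judgement under the co-morbidity clause, so there is a route to exclude these patients. Alternatively, 6.4.3 may be only a shorthand explanation of why the bleeding criteria exist, in which case 5.2 governs and nobody is wrongly enrolled. The affected group is also narrow, and other safeguards apply: a gastroscopy before randomisation (6.2, 6.3.3), calls at 4 and 8 weeks that ask about bleeding (10.2), and weekly review of adverse events (6.7). Section 6.4.3 itself says that human trials have not consistently linked high vitamin E intake to haemorrhage. The screening guideline is not shown and might name past GI bleeding.

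Some of this stands. The group is small and cannot be counted, an attentive investigator may well exclude such a patient, and the safeguards reduce the consequence. They do not remove the contradiction. A discretionary clause does not carry out an unconditional exclusion, and screeners are sent to 5.2 only. Endoscopy may show a current lesion but does not establish a history of bleeding, and the calls come after treatment has begun. If 6.4.3 is shorthand, it overstates the protection actually given, and does so in the section that sets out participant risk. Either reading calls for a correction; they differ only in which section should change.

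**Conclusion.** The concern holds. One of the three bleeding exclusions stated in 6.4.3 is only partly carried into the list used at screening. A patient whose past GI bleed was not severe and not linked to a recent ulcer, with normal clotting and no warfarin, is excluded by one section and admissible under the other.

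This is an inconsistency in eligibility and safety text. It does not touch the sample size, the outcomes or the analysis. The number of participants concerned cannot be derived from the protocol and could be zero. The conclusion rests on the plain wording of 5.2, 6.4.3 and 6.5, and on taking the unseen screening guideline to do what 5.3 says it does. It should be corrected because the protocol gives its own safety reason for the exclusion and the correction is very cheap.

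**What to change.** By default, add any history of gastrointestinal bleeding to the haemorrhage entry in section 5.2 and to whatever screening form is in use. Replace the restated criteria in 6.4.3 with a reference to 5.2, so that only one list exists.

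If the clinical safety lead judges that only severe bleeds or recent ulcers matter, leave 5.2 as it is and narrow 6.4.3 to match it. The choice is clinical, but it should be made explicitly and the two sections should then agree.

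The default costs one phrase in 5.2, one line on the form and a cross-reference in 6.4.3, with possibly a few more screen failures. Narrowing 6.4.3 costs one sentence and does not affect recruitment.

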6.5 Recruitment and Screenings

Potential participants with suspected pharyngeal stricture where endoscopic dilatation is indicated will be identified and screened for eligibility at Swallow Clinic (A/[name], [name], [name]) or during post-cancer-treatment visits at Cancer Care Centre (A/[name], A/[name]).

SSQ will be used as a clinical assessment to quantify swallow impairment in post-laryngectomy patients. Score >234 will indicate pharyngeal dysphagia and suitability for this study. Potential participants will then be screened for exclusion criteria (see 5.2).

Screening will be completed after consent as presence of a stricture can only be truly identified during endoscopy while patient is sedated. If participant is eligible they will be enrolled into the study.

6.6 Informed Consent Process

Eligible individuals will be invited to participate in the study at the time of clinic appointment. If the invitees express interest, they will be given a copy of the PIS/CF and continue the discussion on the same day or a later appointment. The initial discussion will be approximately 30 minutes. Invitees who wish to have more time will be encouraged to take the PIS/CF home and contact the investigators at a later date.

Potential participants will typically have 2 or more weeks to consider participation, as they await the date of their Day Surgery Admission for endoscopic dilatation. Consent can be obtained on the day of their endoscopy but before sedation.

6.7 Adverse Event Reporting

Weekly research meeting will be held by investigators to review the study progress and adverse events. Adverse events will be handled according to the guidelines published in: "*Safety monitoring and reporting in clinical trials involving therapeutic goods.(2016) Canberra: National Health and Medical Research Council*".

6.8 Serious Adverse Event Reporting

All serious adverse events as defined in "*Safety monitoring and reporting in clinical trials involving therapeutic goods.(2016) Canberra: National Health and Medical Research Council*" will be reviewed by the DSMB panel as well as reported to ethics committee within 24 hours.

6.9 Data Safety and Monitoring Board

The National Statement on Ethical Conduct in Human Research (2007) permits monitoring arrangements to be commensurate to the risk, size and complexity of the trial. This trial involves TGA approved substances with known risk profiles, is small and single centre, and does not involve interim analysis. Investigators will review and discuss study progress during weekly research meetings and study coordinator will prepare a report monthly to A/[name] to be reviewed at monthly meeting of the SESLHD Quality use of medicine committee.

7 RANDOMIZATION AND BLINDING

Patients will be randomised during the first endoscopic session following stricture confirmation and endoscopic dilatation (screened and consented prior).

- Ratio 1:1
- blocked randomization with random block sizes

- stratified by 1) treatment naive and 2) previous dilatation(s). Established strictures, which have been dilated previously, may behave differently to those undergoing index dilatation

To ensure double blinding is maintained, blinding of the study medication and dispensing will be managed by Clinical Trials Senior Pharmacist at the hospital pharmacy independent of the study team.

8 STATISTICAL CONSIDERATIONS

8.1 Sample Size Calculation

The sample size of 40 patients for this pilot is based on the number of patients we estimate to recruit over the course of 12 months and maintain the study within budget.

8.2 Statistical Analysis Plan

This is a pilot study aiming to evaluate the feasibility of a full-scale project as such we will assess the following:

- 1) Exclusion/enrolment rates
- 2) Withdrawal rate
- 3) Tolerance to trial medication
- 4) Compliance to therapy
- 5) Data integrity
- 6) Protocol violations and trial completion rate
- 7) Dilatations required
- 8) Adverse Events

Treatment efficacy will be evaluated however the goal is to estimate the trajectory of change of the two continuous outcome variables (SSQ and Pharyngeal Compliance) within subjects from immediately post-dilatation out to 12months. These estimates will help to determine required sample size to show clinically relevant effect and design a full-sized trial competitive for Cat 1 funding.

Outcome measures

Primary: Dysphagia symptom severity - assessed by SSQ (see above) at baseline before dilatation and every 3 months.

Secondary: Pharyngeal compliance assessed by EndoFLIP at 12 months (see above);

9 STORAGE AND ARCHIVING OF STUDY DOCUMENTS

All data will be digitally stored on a secured computer hard drive. Completed questionnaires, endoscopy reports, case report forms will be stored in a locked cabinet inside research office.

The data will be stored for 15 years following publication according to guidelines in case results are challenged or audits are conducted. The data will be securely destroyed according to institutional guidelines using secure document disposal services this will include optical storage media such as CD/DVD. Files on hard drives will be permanently deleted.

10 APPENDICES

10.1 EndoFLIP system and protocol

Strictures of the pharyngo-oesophageal junction (POJ) are conventionally diagnosed fluoroscopically as a narrowed contour. However, we have shown recently that fluoroscopic images frequently fail to detect true stenosis in this population [23]. The likely explanation is that the weakened pharyngeal propulsion is insufficient to distend the hypopharynx (even though it and the POJ may be compliant). This either creates a false appearance of a stricture, or paradoxically, in the absence of adjacent distension, a failure to visualise a real stenosis [23]. For this reason, we now measure directly and objectively both luminal dimensions and tissue distensibility of the POJ using EndoFLIP (Crospan Ltd, Galway, Ireland), an impedance planimetry based technique. We have validated this technique as a highly accurate measures the POJ dimensions and distensibility [8].

In brief, the system comprises a catheter with a series of 17 ringed impedance electrodes (5mm apart) inside a cylindrical bag with infinite distensibility (10cm long) (Figure 1). The catheter is passed trans-orally to position the cylindrical bag within the region of interest in the oesophagus, and the bag infused with solution of known conductivity (0.3% saline) from an external controlled syringe pump integral to the system. During the step-wise distension of the bag, multiple cross-sectional areas along the axial length of the bag are accurately calculated from the measured impedance between paired electrodes at each axial site to create a model of bag area and contour shape. The bag also contains one solid-state manometer continuously measuring intra-bag pressure during inflation. This permits determination of the dynamic pressure-volume-area relationship from which distensibility curves are derived. The infusion is stopped at a predetermined pressure of 60mmHg, to avoid accidental dilatation of the measured organ.

Figure 1 EndoFLIP catheter and system console

10.2 Follow up phone interview

At monthly intervals from time of dilatation to 3 months (total 2 phone calls, the first at 4 weeks following enrolment and then at 8 weeks post enrolment.)

The researcher will greet and introduce themselves to participant.

The researcher will explain the purpose of phone call, to assess how the participant is tolerating medication on post dilatation for stricture trial. The researcher will inform the patient that that notes will be taken during the phone call to ensure that there is an accurate record of any issues or concerns raised.

Researcher will ask patient

- i. If they have experienced any side effects from medication?
- ii. If they have experienced any unexpected or severe bleeding for example prolonged nose bleed, or prolonged bleeding from relatively minor injury.
- iii. If they have been able to comply with dosing as prescribed
- iv. If they have commenced any new medication or supplement since the last contact
- v. If they have any concerns with continuing on the trial
- vi. If they have any feedback regarding the medication or trial that they would like us to consider

The researcher will then check that the patient has adequate numbers of medication.

Finally, the researcher will confirm the date and time of the next phone consult. At the 8 week phone call the researcher will confirm the date for the 12 week visit. Which can either be done at the Swallowing Clinic, a Cancer Care Centre follow up appointment or if they are referred from an external centre (or by patient choice) the SSQ can be posted with an addressed return envelope.

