6.2 Study Plan

Following informed consent, but prior to randomisation, participants will undergo a baseline diagnostic endoscopy as per 'standard of care'. While sedated the compliance (elasticity) of their pharynx will be assessed using EndoFLIP (see 6.3.2 below) and they will undergo an endoscopic dilatation procedure. If baseline compliance of the POJ is reduced ie: a fibrotic stricture is present, the EndoFLIP assessment will be repeated after dilatation and participants will be randomised to receive either 1) PTX + VitE or 2) Placebo after the dilatation. Endoscopy and dilatation is part of routine care and is indicated regardless whether a patient is participating in the study.

NOTE: In case when dilatation endpoint is not met during the first dilatation (see 6.3.3 below), endoscopy will be repeated until one of the endpoints is met and then post-dilatation EndoFLIP assessment will be performed and participant will be randomized and commence study medication. Repeated incremental dilatation are part of routine care (see 6.3.3 below).

Following discharge, patients will be followed-up by a monthly phone call while on study medication for 3 months (see telephone script in appendix). From 3 to 12 months participants will have the option to attend a 'Swallow clinic' every 3 months where they will return unused medication and their swallowing function will be assessed by SSQ. Otherwise medication and SSQs will be returned by posting ad reply-paid envelopes to the participants.

Repeat endoscopy with EndoFLIP will be performed at 12 months to assess the change in POJ compliance from the immediate post-dilatation assessment.

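### The scripted safety questions end with the 8-week call, so patients whose 12-week contact is postal have no stated enquiry for the last 4 of 12 treatment weeks, and the contact clock is unsettled

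*Protocol*

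**What the plan says.** Protocol section 4.4 gives study medication "three times a day for 12 weeks". Section 6.2 states that "patients will be followed-up by a monthly phone call while on study medication for 3 months" and refers to the appendix for the script, but gives no number of calls.

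The script in section 10.2 opens with "At monthly intervals from time of dilatation to 3 months" and then specifies "total 2 phone calls, the first at 4 weeks following enrolment and then at 8 weeks post enrolment". It continues: "At the 8 week phone call the researcher will confirm the date for the 12 week visit". That visit may take place at the Swallowing Clinic or at a Cancer Care Centre appointment. For external referrals, or if the patient prefers, "the SSQ can be posted with an addressed return envelope".

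The six script questions (i to vi) cover side effects, unexpected or severe bleeding, dosing compliance, new medication or supplements, concerns about continuing, and feedback. They appear nowhere else in the protocol. For the three-monthly contacts, section 6.2 states only that unused medication is handed back and the SSQ completed, in clinic or by post.

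Section 8.2 lists eight feasibility assessments. They include "3) Tolerance to trial medication", compliance to therapy (item 4) and adverse events (item 8).

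**The concern.** A pilot of 40 patients is meant to tell the full trial how well the combination is tolerated. That depends on asking patients about harms throughout treatment. The SSQ is a 17-item swallowing inventory and does not ask about side effects, bleeding or new drugs. Where it is posted in place of the 12-week visit, the last stated enquiry is the 8-week call. Events after that call reach the data only if the patient volunteers them.

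Non-serious events are the ones most easily lost in this way. Bleeding is a risk the protocol itself singles out in the exclusions (5.2) and in the vitamin E risk text (6.4.3). Question iv is also the only stated check during treatment on new medication and on the vitamin E abstinence required in 5.1.

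The second difficulty is the clock. Calls are tied to time on medication in one place, and to dilatation and enrolment in another. These dates coincide only if drug starts at the session at which the patient is enrolled.

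**Working it through.** **1. The number of calls.** Monthly contacts over 12 weeks fall at weeks 4, 8 and 12. If the week-12 contact is the 12-week visit, 3 − 1 = 2 calls remain, which reproduces the figure in section 10.2. If every monthly contact in section 6.2 is meant as a call, the count is 3. The text allows both readings.

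**2. What each contact asks, as stated.**

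| Contact | Stated content | Side effects, bleeding, new drugs asked? |
|---|---|---|
| Week 4 call | Questions i to vi | Yes |
| Week 8 call | Questions i to vi | Yes |
| Week 12, in person | SSQ, return of unused medication | Not stated, but staff see the patient |
| Week 12, postal | SSQ, return of unused medication | No |

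**3. Interval after the last stated enquiry, drug starting at enrolment.** (12 − 8)/12 = 4/12 = 33% of treatment.

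**4. Effect of the time origin.** Let d be the delay in weeks from enrolment to first dose. The calls then fall at treatment weeks 4 − d and 8 − d, and the time after the last call is 12 − (8 − d) = 4 + d weeks.

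Inputs for d:
- Section 6.5 enrols the patient once endoscopy has confirmed eligibility, which can be read as the first session.
- Section 6.2 delays randomisation and study medication until a dilatation endpoint is met.
- Section 7 places randomisation at the first session.
- Section 6.3.3 repeats dilatation every 2 weeks and cites a median of 3 per patient from earlier pilot data.

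If enrolment is at session 1 and drug starts at session n, then d = 2(n − 1).

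| Sessions n | Delay d (weeks) | Calls at treatment week | Weeks after last call |
|---|---|---|---|
| 1 | 0 | 4 and 8 | 4 of 12 (33%) |
| 2 | 2 | 2 and 6 | 6 of 12 (50%) |
| 3 | 4 | 0 and 4 | 8 of 12 (67%) |

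If the 12-week contact is also counted from enrolment, it falls at treatment week 12 − d. With d = 4 that is week 8, before treatment ends. A patient seen in person would then have 4 weeks after the last contact of any kind.

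The protocol does not give the share of patients who will use the post, and gives no event rate for weeks 8 to 12. The number of missed events therefore cannot be computed.

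**The case against.** The strongest reply is that the two sections fit together. Section 6.2 gives no count and defers to the script, and the script's third monthly contact is the 12-week visit. This stands. A reader might infer a flat contradiction between monthly calls and two calls, but the text does not force it.

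A reader might also infer that late adherence goes unrecorded. It does not: unused medication comes back in clinic or by post and reflects the whole course, although no tablet count is described.

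Nor does the text support saying that late adverse events go unasked for everyone. In-person patients are seen at week 12, and nothing prevents staff from asking. Sections 6.7 to 6.9 add weekly review, 24-hour reporting of serious events and monthly reports. These describe what happens once an event is known, not when patients are asked, so they weaken the point without answering it.

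The 67% figure should not be read as the plan's actual gap. It needs enrolment at the first session and a 4-week delay to first dose. Section 6.2 ties the calls to time on medication, and a tolerance question makes little sense at treatment week 0, so the intention was probably different. The text still does not settle it.

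Finally, the schedule is the same in both blinded arms, and no size can be put on any under-count.

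**Conclusion.** The point holds in a limited form. As written, patients who use the postal option have no stated enquiry about side effects, bleeding or new medication for the last 4 of 12 treatment weeks (33%), assuming drug starts at enrolment. Non-serious adverse events and intolerance may be under-counted in that interval. By how much is unknown. For adherence the gap is only partial.

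The time origin is unsettled across sections 6.2, 6.5, 7 and 10.2. With first-session enrolment and an assumed 4-week delay to first dose, 8 of 12 weeks (67%) follow the last call. That is a scenario, not an established figure.

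Contact timing and safety questions are protocol content, so this is not a matter to leave to a separate analysis plan. It is a cheap improvement worth making, and it does not threaten the validity of the trial.

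**What to change.** - Reconcile sections 6.2, 7 and 10.2 on the number of contacts and their time origin, including how enrolment, randomisation and first dose relate when dilatation is repeated.
- Count the follow-up contacts from first dose, so that those at weeks 4, 8 and 12 span the treatment course.
- State that script questions i to vi are asked at the 12-week end-of-treatment contact, by phone when that contact is postal.
- Record a count of the tablets that are already being returned.

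The cost is a wording change and at most 40 × 1 = 40 short calls by existing research staff, reached only if every patient chooses the post.
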